Nasopharyngeal swab samples will be taken for quantitative real-time polymerase chain reaction to make diagnosis of Covid19 (2 repeated tests).

Data collected include time of type of symptoms (cough, fever, dyspnea, conjunctivitis, diarrhea, asthenia, arthralgia) and duration, comorbidities (presence of diabetes, hypertension, cardiovascular disease), PaO2/FiO2 ratio, age, sex, height, weight, triglycerides, complete blood count, D-dimer, lactic acid dehydrogenase (LDH), high-sensitivity C-reactive protein (hs-CRP), albumin, and ferritin. The duration of the follow-up will be 28 days from the patient's hospitalization or until his/her discharge or death.

Primary end-point

The primary end-point is to identify the best predictors of critical coronavirus pneumonia and to realize a simple severity score able to early classify high-risk individuals admitted to Internal Medicine Department for COVID-19 disease, needing an intensive approach.

The evaluated predictors for the score assessment are the following: symptoms duration, type of symptoms (cough, fever and dyspnea), comorbidities (presence of diabetes, hypertension, ischemic heart disease), PaO2/FiO2 ratio, age, sex, body mass index (BMI), triglycerides, white cell count, lymphocyte count, D-dimer, lactic acid dehydrogenase (LDH), high-sensitivity C-reactive protein (hs-CRP), albumin, and ferritin. These parameters were collected at admission.

Sample size calculation

The sample size determination is based on the following considerations:

1) the objective of the study is that of finding the best predictors of severe coronavirus pneumonia outcome;

 the study sample will be constituted by inpatients cases of COVID-19 admitted to Internal Medicine Department of Fondazione Policlinico A. Gemelli IRCCS;

3) in order to test the predictive ability of the developed score the study sample will be split into a fitting population and a validation population by using the internal/validation/data-splitting method 4) the following rule-of-thumb will be considered: the power for a test of a medium-sized partial correlation between y and a predictor, holding all other predictors constant, is approximately .80 if N = 104 + m, where m is the number of predictors (11).

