Starting from the above considerations, and from the hypothesis that about 20 predictors will be evaluated for development of a risk score able to predict the severe coronavirus pneumonia outcome, the population size of the fitting population is set to N = 104+20=124 patients. In the procedure of splitting the data set into a fitting population and a validation population, the 50% of the entire sample will be used for the fitting step and the remaining 50% will be used as a validation population. A sample size of 248 patients will be therefore necessary.

Statistical Analysis

Primary Analysis

The data set will be split into a fitting population and a validation population by using the internal/validation/data-splitting method. The internal/validation/data-splitting method is chosen to limit the possible increase in bias that can occur with other techniques for internal validation such as

Bootstrapping technique if the original study population contains biases. The portion of the population used as fitting population for model development will be chosen randomly. The model will be then tested, in terms of its performance on the remaining validation population. Computation of the C statistic will be used to indicate the discrimination performance of the model. The C statistic represents a measure of the model's performance in terms of the model discrimination ability to separate subjects with different outcomes, and for the logistic model, it is equivalent to the area under the curve of the receiver operating characteristic (ROC) curve associated to the model (12) Values of C between 0.8 and 0.9 will be considered to give an excellent discrimination.

Computation of the probabilities: For each subject, both from the fitting population and the validation population, the probability of the studied outcome will be computed on the basis of the patient's covariate values. Each subject will be therefore characterized by the values of the covariate set, the outcome (coronavirus-severity, 0/1) and by the estimated probability of the outcome.

Computation of the C statistics: For both the fitting and the validation populations, the C statistics will be computed. The accuracy (percentage of true positive and negative on the total subjects) of the prediction model will be also computed.

Procedure repetition: The entire procedure (data splitting, model fitting, probability computation) will be repeated 200 times.

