Secondary analyses include the use of other classification procedures to compare results from the primary analysis. One of the classification procedures that will be used to classify patients with severe and non-severe coronavirus pneumonia outcome, on the basis of the collected variables, will be the Partial Least-Squares Discriminant *Analysis (PLS-DA)*. A cross validation approach will be followed and the optimal model with the optimal number of PLS components will be derived. The Q2 value, the ROC AUC and the derived misclassification error, by the classification Youden criterium, will be used to quantify the classification goodness. A permutation approach, including 1000 random permutations, will be used in order to associate a P level to the obtained Q2 value. Random forest classification procedure, which is based on learning algorithms, will be also tested following the same procedure of splitting the entire sample into a training set and a test set. Univariate analyses studying the association between severity and predictors will be conducting using Chi-Squared tests or Fisher exact tests when appropriate or univariate logistic regression models for quantitative variables. Secondary analyses will have only an explorative purpose.

REFERENCES

5) Dong L et al. Discovering drugs to treat Coronavirs Disease 2019 (COVID-19). Drug Discov Ther 2020

7)Womg CK, et al. Plasma inflammatory cytokines and chemokines in severe acute respiraoty syndrome. Clin Exp Immunol 2004;

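### PLS-DA is validated under a different and under-specified scheme and cut-off rule from logistic regression and random forest, so the planned comparison is not like-for-like

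*Combined protocol and SAP*

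**What the plan says.** The Secondary analyses section states its aim as the use of "other classification procedures to compare results from the primary analysis". It then describes two of them.

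- **PLS-DA.** "A cross validation approach will be followed and the optimal model with the optimal number of PLS components will be derived". Performance is summarised by Q2, ROC AUC and the "derived misclassification error, by the classification Youden criterium". The section does not give the number of folds, the patients on whom these figures are computed, whether tuning is nested, or the data on which the cut-off is set.
- **Random forest.** It is tested by dividing the whole sample into a training part and a test part.

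For the primary logistic model, the Sample size calculation section says that "the 50% of the entire sample will be used for the fitting step and the remaining 50% will be used as a validation population". The Primary Analysis section repeats this split 200 times and reports the C statistic and accuracy in both halves. It states no probability cut-off for accuracy. A reduced logistic model is then formed from the variables that looked most important in the full-model results, and the splitting procedure is run again on the same patients.

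All secondary analyses are declared exploratory.

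**The concern.** A comparison of classifiers separates method from procedure only if each is trained on the same amount of data, tested on patients not used to tune it, and judged at a cut-off chosen by the same rule. As written, PLS-DA differs from logistic regression on the first and third of these, and the plan is silent on the second. A difference in AUC or misclassification could then come from the resampling scheme or the cut-off rule, and a reader of the results could not tell which. What is at stake is the interpretation of the secondary comparison. The score itself is not at stake, because its coefficients come from the reduced logistic model.

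**Working it through.** **1. The plan's own figures.** The protocol assumes that "about 20 predictors will be evaluated for development of a risk score" and applies a rule under which power "is approximately .80 if N = 104 + m, where m is the number of predictors". With m = 20, N = 104 + 20 = 124 for the fitting half, and 124 / 0.50 = 248 in total. Both figures reproduce.

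**2. The schemes side by side.**

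| | Logistic regression | Random forest | PLS-DA |
|---|---|---|---|
| Training data | Random 124 of 248 | A training part; ratio not restated | Cross-validation; folds not stated |
| Data scored | Other 124 (and fitting half) | Test part | Not stated |
| Data for tuning | Variables for reduced model taken from full-model results, same patients | Not stated | Components by cross-validation; nesting not stated |
| Cut-off for error | None stated | None stated | Youden; data not stated |

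**3. Simulation assumptions.** The plan gives no outcome rate, effect sizes or folds, so these are assumed. Simulation A: 248 patients; 20 normal predictors with pairwise correlation 0.2, five of them informative; outcome rate 10% to 40%; best attainable AUC about 0.75 or 0.85, plus a null case; 200 data sets with six 124/124 splits each. PLS-DA used one to six components, chosen by Q2 in 10-fold cross-validation, and was scored in the same folds. Simulation error on a mean AUC is roughly 0.005. Simulation B: 248 patients, 20 independent predictors, 10% to 30% events, 10 folds.

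**4. Training size alone.** Ten-fold cross-validation trains on about 0.9 × 248 = 223 patients, against 124. In simulation A the same 20-predictor logistic model scored 0.016 to 0.038 higher in AUC under cross-validation than under half-splits, with no change of method.

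**5. PLS-DA itself.** Its AUC under its own cross-validation, minus its AUC on 124/124 splits, was -0.01 to +0.02 in simulation A and about +0.03 in simulation B. Choosing components in the scored folds did not inflate AUC materially: the difference from its true AUC was -0.04 to +0.004, and the null value was 0.49 to 0.51.

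**6. Cut-off.** Setting the Youden cut-off on the scored predictions understated PLS-DA error by 0.007 to 0.026 and overstated Youden's J by 0.05 to 0.08 (simulation A). In simulation B, PLS-DA error was 0.04 to 0.06 lower under its own cross-validation than on the splits.

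**7. Effect on the comparison: simulation A, 40% outcome rate, full logistic model.**

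| | Attainable AUC 0.750 | Attainable AUC 0.845 |
|---|---|---|
| PLS-DA AUC, own cross-validation | 0.711 | 0.811 |
| PLS-DA AUC, splits | 0.711 | 0.794 |
| Logistic AUC, splits | 0.677 | 0.786 |
| PLS-DA lead, different schemes | 0.711 - 0.677 = 0.034 | 0.811 - 0.786 = 0.025 |
| PLS-DA lead, same splits | 0.711 - 0.677 = 0.034 | 0.794 - 0.786 = 0.008 |
| Error: PLS-DA own cross-validation minus logistic at 0.5 | 0.327 - 0.358 = -0.031 | 0.254 - 0.281 = -0.027 |
| Error: same splits, Youden set in fitting half for both | 0.360 - 0.372 = -0.012 | 0.292 - 0.289 = +0.003 |

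In the second column, 0.017 of the 0.025 AUC lead comes from the scheme, and the apparent advantage in error disappears. In the first column the scheme does not change the AUC lead.

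**8. Effects in the other direction.** Youden does not minimise misclassification. Against logistic error at an assumed 0.5 cut-off, PLS-DA error was 0.26 to 0.35 versus about 0.16 at a 10% outcome rate, and 0.25 to 0.34 versus 0.21 to 0.24 at 20%.

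For the reduced logistic model, five variables were ranked on all 248 patients before re-splitting (the number five is assumed). Its validation AUC exceeded PLS-DA's cross-validated AUC by between 0.835 - 0.814 = 0.021 (40% rate) and 0.753 - 0.704 = 0.049 (10% rate). It exceeded the reduced model's own true AUC by 0.01 to 0.08, and under the null it showed 0.58 to 0.63 where 0.50 is correct.

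**The case against.** A reader might infer that the plan favours PLS-DA by design. The documents do not support that, for three reasons.

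First, scoring PLS-DA in its own tuning folds is read from silence. The text ties cross-validation to deriving the model and does not say where AUC and error are computed. The random forest sentence, which speaks of also testing by the same splitting procedure, leaves open that PLS-DA is tested on a split too.

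Second, the direction is not established. In simulation A the scheme moved PLS-DA's AUC very little; its lead over the full logistic model was 0.03 to 0.08 under different schemes and still 0.01 to 0.08 on identical splits. Youden error can count against PLS-DA when events are few, and the reduced logistic model gains from variable selection outside the split.

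Third, the consequence is small. The analyses are exploratory, no rule picks the better classifier, and the comparison may be meant as a consistency check.

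All three stand against a claim of directional bias. They do not make the figures comparable. If a held-out test of PLS-DA is intended, the plan should say so. A difference whose sign depends on the outcome rate and on which logistic model is compared cannot be attributed to the method. Exploratory status limits the damage but does not remove the ambiguity.

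**Conclusion.** The point holds as one of comparability and under-specification. As written, PLS-DA has a cross-validation scheme and a Youden cut-off, logistic regression is tested after training on half the sample with no stated cut-off, and random forest is tested on a split. No separate data are named for choosing the PLS components or the cut-off.

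The effect on PLS-DA's AUC is about -0.01 to +0.03 over the two simulations, and its error is understated if the cut-off is set on the scored data. The net direction against logistic regression can go either way. These sizes rest on the assumed outcome rates, predictor correlations, effects, ten folds and five retained variables, none of which the protocol fixes. Severity is minor.

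**What to change.** State in the Secondary analyses section that logistic regression (full and reduced), PLS-DA and random forest are all evaluated on the same 200 random splits. Within each split:

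- choose the number of PLS components, any other tuning values, the variables of the reduced logistic model and the cut-off inside the fitting half only, by cross-validation there where needed;
- use one cut-off rule for all methods, including logistic accuracy;
- report AUC and misclassification in the validation half.

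Summarise methods by the paired difference over splits. Present these differences descriptively, since the 200 splits reuse the same patients and are not independent replicates. Q2 and its permutation test can stay as a description specific to PLS-DA.

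The cost is some programming and no extra data. Reported figures for PLS-DA and for the reduced logistic model may be slightly less favourable.
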